## XI. DATA MANAGEMENT

---

### a) *Data collection in the eCRF*

The eCRF will be designed to ensure that all required data in the protocol are captured.

A Case Report Form (CRF, see Chapter XXI. APPENDICES) will be completed for each subject enrolled into the clinical study. The investigator will review, approve and sign/date each completed CRF; the investigator's signature serving as attestation of his responsibility for ensuring that all clinical data entered on the CRF are complete, accurate and authentic. It will also track any missed, unused, and/or spurious data.

Bepatient EDC platform will be used and is specifically designed for Symbios needs. Bepatient has developed a unique comprehensive eHealth platform which will be used for the purpose of this study. Bepatient electronic system will be used as the sole instrument for the recording and analysis of clinical data related to the safety and efficacy of the investigational device, and respect the compliance with good practices (21 CFR part 11) and in accordance with the General Data Protection Regulation (GDPR). This tool has a Validated system with an access limited to authorized individuals, compliant password policy (unique ID/password combination), eSignature (investigator, data freeze by monitor / data manager), is secure computer-generated, allow time-stamped audit trail and Study records (print option, export module to your tools / CSV / Excel / SAS).

### b) *Source documents*

Entered data in the eCRF must be traceable to source documents. Source documentation is defined as the first time the data appear (original records and certified copies of original records) and may include all clinical records, hospital records, procedural reports, autopsy reports, and any other material that contains original information used for study data collection or adverse event reporting.

Data reported on the e-CRFs should be traceable to source documents. Source documents must be available for review by Symbios personnel and/or applicable local EC and will be used for verification of the data reported on the e-CRFs and adjudication of AEs.

Where copies of the original source document as well as print outs of original electronic source documents are retained, these shall be signed and dated by a member of the investigation site team with a statement that it is a true reproduction of the original source document.

The Investigator must ensure the availability of source documents from which the information on the e-CRFs was derived. In addition, the medical records of study subjects should be marked or flagged in such a way to indicate their participation in the study.

### c) *Data management*

A validated database mentioned above will be in place to store the clinical data information.

SYMBIOS		 symbios  Clinical Investigation Plan	F029.03
Date	27.11.2019		Distribution Informatique pdf
Auteur	BGA		
Contrôle	EBO		
Libération	RAQ		

Once created, it will require a validation of the protocol specific implementation of the EDC. This will be done by Symbios in collaboration with Bepatient prior to the study start.

The Data Management process regarding the data in the eCRF will include all activities related to data handling regarding:

- Data entry & processing (the data will be entered by the appropriate site personnel, listed on the Delegation Task List)
- Data security (the access to the database is secure and based on log in & password details, not accessible to an unauthorized person or individual)
- Data Validation (will ensure the most accurate validated set of data is provided for statistical analysis)
- Data controlling (via a monitor who will verify the accuracy of data entry. Completeness will be checked by authorized personnel at Symbios so that there are no unexplainable empty fields in the eCRF. This is done in order to prevent that data being overlooked by personnel entering the data).
- Database lock (quality control will be performed by the designed Data Manager in order to verify completeness). If the data is validated and no more outstanding queries or discrepancies, the data can be considered as cleaned. At this stage, the database will be locked.

In addition to the above, obvious writing and spelling errors in the eCRF may be corrected without issuing a query.

All comments have to be written in English. Any translation in the CRF should be signed and dated by the investigator.

After receipt of an Adverse Event (AE), the following must be checked immediately:

- Serious Y/N;
- Relationship to procedure/investigational product.

All decisions on the evaluability of the data from each individual subject for the statistical analysis must be made and documented before locking the database. Data will be retained for at least 15 years after investigation closure.

SYMBIOS		 symbios  Clinical Investigation Plan	F029.03
Date	27.11.2019		Distribution Informatique pdf
Auteur	BGA		
Contrôle	EBO		
Libération	RAQ		

## XII. DEVIATIONS FROM THE CLINICAL INVESTIGATION PLAN

### a) *Definition of deviation (ISO 14155: 2020)*

Instance of failure to follow, intentionally or unintentionally, the requirements of the CIP

A study deviation is an event where the investigator or investigation site personnel did not conduct the clinical study according to the Clinical Investigation Plan or Clinical Investigation Agreement.

The investigator is not allowed to deviate from the above-mentioned documents except with prior approval. All deviations shall be documented and explained, regardless the reason for the deviation.

Examples of protocol deviations include but are not limited to the following:

- Failure to obtain informed consent (either signed patient Informed Consent) prior to participation
- Incorrect version of the Patient Informed Consent used
- Failure to obtain EC approval before the start of the study
- Implanted subject did not meet inclusion/exclusion criteria
- Follow-up visit not done
- Adverse events not reported in the required time frame as required by regulation or as specified in the CIP
- Source data permanently lost
- Enrollment of patients during lapse of EC approval

### b) *Request for approval of study deviations*

The investigator shall obtain documented approval from Symbios, before implementation, for any change in or deviation from the Clinical Investigation Plan. In case of study deviations that can affect the subject's rights, safety and well-being or the scientific integrity of the clinical study, approval from the local EC must also be obtained before implementation. The investigator shall timely contact the Clinical Affairs Manager for review of the proposed change/deviation.

Prior approval is not always realistic in situations where unforeseen circumstances are beyond the investigator's control. However, also in these cases, the event is considered a deviation, and shall be reported.

In any emergency situation the investigator shall exercise his judgment to safeguard the subject's interest. Such deviations from the Clinical Investigation Plan do not require the prior approval of Symbios. The investigator shall report the deviation as soon as possible to Symbios and the applicable local EC.

### c) *Reporting requirements for study deviations*

Study deviations should be reported to Symbios via the Study Deviation e-CRF excel table. Relevant information for each deviation will be documented by site personnel and reviewed by the Investigator. Investigators should report the following deviations to Symbios and their reviewing EC:

- Failure to obtain written informed consent
- Deviations to protect the life or physical well-being of a subject in an emergency

SYMBIOS		 symbios  Clinical Investigation Plan	F029.03
Date	27.11.2019		Distribution Informatique pdf
Auteur	BGA		
Contrôle	EBO		
Libération	RAQ		

In addition, Investigators are required to adhere to local EC procedures for reporting deviations. Symbios is responsible for analyzing deviations, assessing their significance, and identifying any corrective and/or preventive actions that may be necessary. Repetitive or serious investigator compliance issues may represent a need to initiate a corrective action plan, which may include suspension of enrollment or termination of the investigator's or site's participation in the study. The deviations will be traced periodically and followed-up by monitor together with the study personal and the PI.

SYMBIOS		 symbios  Clinical Investigation Plan	F029.03
Date	27.11.2019		Distribution Informatique pdf
Auteur	BGA		
Contrôle	EBO		
Libération	RAQ		

### XIII. STATEMENT OF COMPLIANCE

---

This clinical study will be conducted in compliance with the latest version of the Declaration of Helsinki (2013), the international standard ISO 14155, laws and regulations of the countries in which the clinical study is conducted, including data protection laws, the Clinical Investigation Agreement and the Clinical Investigation Plan. At the EU level, the study will also be compliant with Regulation (EU) 2016/679 (General Data Protection Regulation), and a new EU Regulation on medical devices (MDR 2017/754), which has entered into force on May 25, 2017, with a transition period. The MDR will fully apply in EU Member States from May 26, 2021 and will replace the existing directives and will apply for this study for reporting of serious adverse events and device deficiencies.

Symbios and participating investigators will conduct the clinical investigation in accordance with the ethical principles described above and will be compliant with International Conference and Guidance and any regional or national regulations, as appropriate.

The clinical investigation (CIP & PIC) shall begin upon local EC approval; as written approval from competent authority is not required (PMCF study). Approval of both the protocol and the consent form must be obtained before any participant is enrolled. Other documents that are referred to this Clinical Investigation Plan in the APPENDICES and are listed below, will be made available upon request: • Instructions for Use • Case Report Forms • Monitoring Plan • Data Management Plan • Statistical Analysis Plan

Any amendment to the protocol will require review and approval by the EC before the changes are implemented to the study. If the EC imposes any additional requirements (e.g. safety reports, progress reports etc.), Symbios will prepare the required documents and send them to the investigator for reporting to the EC. Investigators must inform Symbios of any change in status of EC approval once the investigation site has started enrolment. If any action is taken by an EC with respect to the investigation, that information will be forwarded to Symbios by the respective investigator.

Pediatric, legally incompetent, or otherwise vulnerable patients are not eligible for the study.

Symbios will maintain appropriate clinical study liability insurance coverage if required under German applicable laws and regulations and will comply with applicable law and custom concerning specific insurance coverage.

A clinical study agreement between sponsor, institution and the Principal Investigator will be executed prior to any clinical activities.

SYMBIOS		 symbios  Clinical Investigation Plan	F029.03
Date	27.11.2019		Distribution Informatique pdf
Auteur	BGA		
Contrôle	EBO		
Libération	RAQ		

## XIV.AMENDMENTS TO THE CIP

---

The CIP, CRFs, informed consent form, or other clinical investigation documents such as instructions for use shall be amended as needed throughout the clinical investigation in accordance with written procedures for the control of documents and document changes.

Documentation of changes shall include a description of the changes, justification of the changes and their potential impact on the performance, effectiveness, safety or other endpoints, and identification of the affected documents.

The investigator could propose any appropriate modification(s) of the Clinical Investigation Plan or product use. Symbios will review this proposal and decide whether the modification(s) will be implemented to the CIP. Symbios will submit any significant amendment to the Clinical Investigation Plan, including a justification for this amendment, to the appropriate EC and to the Principal investigator. The version number and date of amendments shall be documented. The PI will only implement the amendment after approval of the EC, and sponsor. Furthermore, co-investigators shall sign any approved amendment for agreement.

If the amendment impacts the integrity of the clinical investigation, the data collected before and after the amendment shall be analyzed statistically to assess the effect of the amendment on performance, effectiveness or safety analysis. This analysis shall be included in the clinical investigation report.

SYMBIOS		 symbios  Clinical Investigation Plan	F029.03
Date	27.11.2019		Distribution Informatique pdf
Auteur	BGA		
Contrôle	EBO		
Libération	RAQ		

## XV. PATIENT INFORMATION PROCESS

---

The Patient Information Consent form will consist of an information form and a signature form. Subject selection will be based on the defined inclusion/exclusion criteria. Each patient who meets the inclusion criteria will be informed about this study before any data is collected. This information will be given during the preoperative consultation, during which the surgeon will give to the patient the information letter & the signature form (See. Chapter XXI. APPENDICES. D. PATIENT INFORMATION SHEET), and will be available to answer any questions.

This information letter will contain information regarding study design and investigational devices. It will explain risks/benefits for patients willing to participate in the study. It will also give information on the planned schedule of assessment, and follow-up visits up to 2 years. Subjects willing to participate will then sign the consent form, which will be the start of the enrolment process, prior to randomization process for ARM 1: ORIGIN PS or ARM 2: VANGUARD PS.

At any time and during the course of the study, each subject has a real freedom of choice to participate in this study. If he/she agrees, he/she has the right to access and rectify his/her data but also the right to withdraw his/her consent when he/she wishes, as simply as he/she has decided to grant it. This includes the right to erase the collected data and the right to object to the use of such data.

The process of how the Patient Informed Consent form has been obtained, will be described in the patient's medical file.

SYMBIOS		 symbios  Clinical Investigation Plan	F029.03
Date	27.11.2019		Distribution Informatique pdf
Auteur	BGA		
Contrôle	EBO		
Libération	RAQ		

## XVI. ADVERSE EVENTS, ADVERSE DEVICE EFFECTS AND DEVICE DEFICIENCIES

---

For the purpose of this study, Symbios will classify each category of adverse events based to the ISO 14155: 2020.

### A. Adverse event

Untoward medical occurrence, unintended disease or injury, or untoward clinical signs (including abnormal laboratory findings) in subjects, users or other persons, whether or not related to the investigational medical device and whether anticipated or unanticipated

**Note 1:** This definition includes events related to the investigational medical device or the comparator.

**Note 2:** This definition includes events related to the procedures involved.

**Note 3:** For users or other persons, this definition is restricted to events related to the use of investigational medical devices or comparators.

### B. Adverse Device Effect

Adverse event related to the use of an investigational medical device

**Note 1:** This definition includes adverse events resulting from insufficient or inadequate instructions for use, deployment, implantation, installation, or operation, or any malfunction of the investigational medical device.

**Note 2:** This definition includes any event resulting from use error or from intentional misuse of the investigational medical device.

**Note 3:** This includes 'comparator' if the comparator is a medical device.

### C. Serious adverse events

Adverse event that led to any of the following:

- a) death,
- b) serious deterioration in the health of the subject, users, or other persons as defined by one or more of the following:
  1. a life-threatening illness or injury, or
  2. a permanent impairment of a body structure or a body function including chronic diseases, or
  3. in-patient or prolonged hospitalization, or
  4. medical or surgical intervention to prevent life-threatening illness or injury, or permanent impairment to a body structure or a body function,

SYMBIOS		 symbios  Clinical Investigation Plan	F029.03
Date	27.11.2019		Distribution Informatique pdf
Auteur	BGA		
Contrôle	EBO		
Libération	RAQ		

c) foetal distress, foetal death, a congenital abnormality, or birth defect including physical or mental impairment

**Note 1:** Planned hospitalization for a pre-existing condition, or a procedure required by the CIP, without serious deterioration in health, is not considered a serious adverse event.

## D. Serious health threat

Signal from any adverse event or device deficiency that indicates an imminent risk of death or a serious deterioration in the health in subjects, users or other persons, and that requires prompt remedial action for other subjects, users or other persons

**Note 1:** This would include events that are of significant and unexpected nature such that they become alarming as a potential serious health hazard or possibility of multiple deaths occurring at short intervals.

## E. Serious adverse device effect

Serious adverse device effect which by its nature, incidence, severity or outcome has not been identified in the current risk assessment

**Note 1:** Anticipated serious adverse device effect (ASADE) is an effect which by its nature, incidence, severity or outcome has been identified in the risk assessment.

## F. Unanticipated Serious Adverse Device Effect

Serious adverse device effect which by its nature, incidence, severity or outcome has not been identified in the current risk assessment

**Note 1:** Anticipated serious adverse device effect (ASADE) is an effect which by its nature, incidence, severity or outcome has been identified in the risk assessment.

## G. Device Deficiency

Inadequacy of a medical device with respect to its identity, quality, durability, reliability, usability, safety or performance

**Note 1:** Device deficiencies include malfunctions, use errors, and inadequacy in the information supplied by the manufacturer including labelling.

**Note 2:** This definition includes device deficiencies related to the investigational medical device or the comparator.

## H. Regulatory requirements for reporting

SYMBIOS		 symbios  Clinical Investigation Plan	F029.03
Date	27.11.2019		Distribution Informatique pdf
Auteur	BGA		
Contrôle	EBO		
Libération	RAQ		

An Unanticipated Adverse Device Effect (UADE) is defined as any serious adverse effect on health or safety or any life-threatening problem or death caused by, or associated with, a device, if that effect, problem, or death was not previously identified in nature, severity, or degree of incidence in the investigational plan, or any other unanticipated serious events associated with the ORIGIN System that relates to the rights, safety, or well-being of patients. All unanticipated adverse device effects must be reported to the Sponsor no later than 24 hours after it occurs.

The following list of safety outcomes should be collected in the eCRF case report form which will trigger a notification to Symbios regulatory department via [[contact]](mailto:[contact]):

- Serious Adverse Events (SAEs)
- Unanticipated Adverse Device Effects (UADEs)
- Devices deficiencies
- Non-serious Adverse Events related to the device or study procedure
- Secondary surgical procedures or revisions
- Surgical complications

All above-mentioned Adverse events will be reported in the final report of the Clinical Investigation.

In accordance with the European Medical Device Directive (MDR), ISO 14155 and with MEDDEV 2.12/1, any serious adverse event, related to the device under evaluation, will be announced by the manufacture:

- To its Notified Body and
- To the relevant competent authority in Germany.

SYMBIOS		 symbios  Clinical Investigation Plan	F029.03
Date	27.11.2019		Distribution Informatique pdf
Auteur	BGA		
Contrôle	EBO		
Libération	RAQ		

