### C. Risks associated with participation in the clinical investigation

There are possible risks and side effects connected to the ORIGIN & VANGUARD implants (as described in the IFU), but the risks are similar to those for an implant of the ORIGIN & VANGUARD without participation in this study. The risks are known and consistent with the state of the art.

Clinical data to date for ORIGIN system are analyzed at short-term follow-up and need to be monitored at medium and long-term (up to 10 years).

Risks and events will be continuously monitored, assessed and documented by the investigator. Instructions for Use is a reference for the list of anticipated adverse events which may be associated with the use of the ORIGIN & VANGUARD System.

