### D. Anticipated adverse events assessment

Adverse effects of the ORIGIN® knee prosthesis are similar to other total knee prostheses on the market.

The expected anticipated adverse events in knee replacement surgery are:

- Displacement and loosening (wear, lysis) of the prosthesis
- Patellar component dislocation, tibial insert component disassociation, femorotibial luxation instability, malalignment, malposition
- Pain, stiffness
- Infection
- Venous thrombosis and pulmonary embolism
- Cardiovascular disorders
- Hematoma
- Delayed wound healing
- Grating sounds in the friction pairs, clicking sensation between post-cam (Tibia Insert plot and Femoral cam), soft tissue impingement, patellar component clunk syndrome
- Implant breakage
- Periprosthetic fracture
- Other effects not known to date or not scientifically established

The list of reportable adverse events in the Adverse Event Form is in explained in the XVI.ADVERSE EVENTS, ADVERSE DEVICE EFFECTS AND DEVICE DEFICIENCIES.

The following list of safety outcomes should be collected in the eCRF case report form which will trigger a notification to Symbios regulatory department via [[contact]](mailto:[contact]):

SYMBIOS		 symbios  Clinical Investigation Plan	F029.03
Date	27.11.2019		Distribution Informatique pdf
Auteur	BGA		
Contrôle	EBO		
Libération	RAQ		

- Serious Adverse Events (SAEs)
- Unanticipated Adverse Device Effects (UADEs)
- Devices deficiencies
- Non-serious Adverse Events related to the device or study procedure
- Secondary surgical procedures or revisions
- Surgical complications

SYMBIOS		 symbios  Clinical Investigation Plan	F029.03
Date	27.11.2019		Distribution Informatique pdf
Auteur	BGA		
Contrôle	EBO		
Libération	RAQ		

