### C. Randomization

There are three major identified barriers for randomized clinical trials on medical devices, namely: (1) randomization, including timing of assessment, acceptability, blinding, choice of the comparator group and considerations on the learning curve; (2) difficulties in determining appropriate outcomes; and (3)

SYMBIOS		 symbios  Clinical Investigation Plan	F029.03
Date	27.11.2019		Distribution Informatique pdf
Auteur	BGA		
Contrôle	EBO		
Libération	RAQ		

the lack of scientific advice, regulations and transparency. In order to build a powerful clinical study, randomization will be applied and patients will receive equal information regarding both prostheses treatment. The randomization procedure will be unpredictable so that investigators cannot guess the next subject's group assignment based on prior treatment assignments. The study will not be blinded, anyhow all attempt will be chosen to prevent bias regarding PROMs data collection and surgeon reported scores.

The study is a randomized trial with two arms:

- Arm 1/ Device under evaluation: Group of 70 subjects who will undergo a surgery with the ORIGIN PS System
- Arm 2/Comparative device: Group of 70 subjects who will undergo a surgery with the VANGUARD System Cf. CHAPTER. XXI. APPENDICES C. RANDOMIZATION FLOW CHART

The randomization will be performed via a secure unique comprehensive eHealth platform named Bepatient which will be used for the purpose of this study, as a live electronic case report form or eCRF. Additional data are displayed in Section XXI. APPENDICES. F. BEPATIENT DATA HANDLING

Bepatient eCRF ensures the respect of the compliance with good practices (21 CFR part 11) and in accordance with the General Data Protection Regulation (GDPR). Authorized site personnel as indicated on the Delegation Task List, will be trained on the use of the system and will be provided with a username and password to access the system in a limited and secure way. CRFs will be implemented to capture the data for each enrolled subject as required by the protocol.

The study methods include the following measures to minimize potential sources of bias:

- The enrolment is controlled and tracked in the eCRF (external partner) to avoid introduction of bias in the trial
- A dedicated Vigilance department will review all deaths and safety endpoint related adverse events

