#### *c) Analysis of clinical data and Safety outcomes*

The rate of serious adverse events (SAE) and Unanticipated Adverse Device Effects (UADEs) during the study will be presented using the proportions of patients experiencing one or more of each SAE and UADE. All serious and non-serious adverse events will be characterized in terms of severity and relatedness to the operative procedure and device. Additionally, the percent of patients requiring one or more secondary surgical procedures relating to the original procedure will be presented. Data will be analyzed for all patients enrolled in this observational study.

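### The eCRF safety list limits non-serious adverse events to related ones, while the analysis section promises all of them by relatedness; the two should be aligned, identically in both arms

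*Combined protocol and SAP*

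**What the plan says.** Sections VI.D and XVI.H carry the same six-item list, introduced by "The following list of safety outcomes should be collected in the eCRF case report form which will trigger a notification to Symbios regulatory department". Serious adverse events are listed without qualification. The item for non-serious events is qualified: "Non-serious Adverse Events related to the device or study procedure". Surgical complications and secondary procedures or revisions are also listed, without a relatedness condition.

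Two sentences tie this list to what is recorded and reported. Section VI.D says "The list of reportable adverse events in the Adverse Event Form is in explained in the XVI", so it sends the reader to chapter XVI for what belongs on the adverse event form. After the list, section XVI.H says "All above-mentioned Adverse events will be reported in the final report of the Clinical Investigation".

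The definition and the analysis are wider. Section XVI.A defines an adverse event "whether or not related to the investigational medical device and whether anticipated or unanticipated". Section X.c says "All serious and non-serious adverse events will be characterized in terms of severity and relatedness to the operative procedure and device".

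On assessment, section VII.C says "The study will not be blinded, anyhow all attempt will be chosen to prevent bias", and section V.C says "Risks and events will be continuously monitored, assessed and documented by the investigator". No section states who judges relatedness before an event is entered. The synopsis lists complications and revision rate, ORIGIN versus VANGUARD PS, among the secondary endpoints.

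**The concern.** A table of non-serious events by relatedness needs both columns. If the site follows the list as written, unrelated non-serious events need not be entered, and the unrelated column is incomplete by design. The reader of the final report could not tell a low count of unrelated events from a rule that did not ask for them.

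The second issue is comparability. Judging whether an ache or a swelling is related to the device or the procedure takes discretion, and in an open-label trial that discretion is exercised with the implant known. If relatedness influences whether an event is written down, and not only how it is labelled afterwards, a different habit of attribution in each arm would appear as a different event count. A recorded relatedness field would let a reader see such a habit; a condition on recording hides it.

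**Working it through.** There is no figure in the plan to reproduce, so the main check is textual.

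**Step 1: scope of each section for non-serious events**

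| Section | Scope |
|---|---|
| XVI.A, definition | related and unrelated |
| X.c, analysis | all, split by relatedness |
| VI.D and XVI.H, eCRF list | related to device or study procedure |
| XVI.H, final report | the listed categories |

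The first two rows and the last two do not match. Within the list, serious events carry no relatedness qualifier and non-serious events do, so the qualifier narrows the scope.

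**Step 2: is there another route for unrelated non-serious events?**

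- Section VIII.F, attempted procedures: adverse events are collected with no relatedness condition, but only for subjects in whom ORIGIN was not implanted, and for 30 days.
- Section VIII.F, 1-year and 2-year visits: complications go on the adverse event form with no relatedness condition, but the term is not defined. The safety heading at both visits names ORIGIN only, although the 2-year text covers revisions in both arms.
- Surgery data (section VIII.F): perioperative complications are collected for both devices.
- Section XI.c: seriousness and relationship are checked once an event has been received. This governs received events and does not say which events are to be sent.

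These routes cover part of the ground. None is a general instruction to record unrelated non-serious events.

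**Step 3: could recording differ by arm, and by how much?**

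Let r be the true risk of a non-serious event, equal in both arms, and s1 and s2 the shares judged related in the two arms. If only related events are recorded:

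recorded risk = r × s, and artefactual gap = r × (s2 − s1).

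The documents give neither r nor s for these events. The rows below are assumptions that show how the gap behaves; they are not estimates for this trial. The arm size of 70 is from section VII.C.

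| r | s1, s2 | Recorded risks | Gap | Patients of 70 |
|---|---|---|---|---|
| any | equal | equal | 0 | 0 |
| 20% | 40%, 60% | 8%, 12% | 4 points | 70 × 0.04 = 2.8 |
| 50% | 40%, 60% | 20%, 30% | 10 points | 70 × 0.10 = 7 |
| 20% | 30%, 70% | 6%, 14% | 8 points | 70 × 0.08 = 5.6 |
| 50% | 30%, 70% | 15%, 35% | 20 points | 70 × 0.20 = 14 |

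The nearest figure in the documents is the 3.25% postoperative complication rate without revision in the sponsor's ongoing ORIGIN study (section IV.B). With a 20-point difference in attribution the gap is 0.0325 × 0.20 = 0.65 points, or 70 × 0.0065 = about 0.5 patient. That rate may itself reflect a narrow recording rule, so it does not bound the risk from above.

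**The case against.** A reader might infer something stronger: that a non-serious event reaches the eCRF only after an unblinded investigator has judged it related, that all other non-serious events leave no record, and that the comparison of complications is biased beyond repair. The documents do not support this.

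- The list contains no word of exclusion. It sits under regulatory reporting and doubles as the trigger for notifying the sponsor, so it can be read as a notification list.
- Section XI.c places the relationship check after an event is received, which suggests relatedness is meant to be recorded.
- Surgical complications and revisions are listed without the condition, so much of the complications endpoint does not depend on the non-serious item.
- Calling an event expected does not exclude it. Section XVI.A covers anticipated events, section VI.D names pain, stiffness and clicking among them, the list also admits events related to the study procedure, and section XVI.B includes the comparator.
- Section X.c promises patient proportions for serious events, unanticipated device effects and secondary procedures. None of these passes through the non-serious item.
- Source records are retained and can be used for adjudication (section XI.b), so omissions might be partly recoverable.
- The case report form and adverse event form are separate documents. What they capture is not known here.

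All of this stands, and it limits the claim. It does not remove the mismatch. The text says the listed outcomes are to be collected, section VI.D refers to chapter XVI for what goes on the form, and the final report is tied to the listed events. Even if the list is only a notification list, the plan has no clear instruction on which non-serious events to record.

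**Conclusion.** The point holds as an inconsistency with a practical consequence. Under sections VI.D and XVI.H as written, the relatedness split of non-serious events promised in section X.c would be incomplete. Serious events, unanticipated device effects and revisions are not affected.

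A difference in recording between arms is possible because the study is unblinded, but it is a risk of unknown size. It requires that the site treats the list as the recording rule and that attribution differs by arm; with equal attribution it is zero. None of the illustrative gaps above is evidence about this trial. The unseen forms might already capture more than the list says, in which case the text alone needs correcting. This is a cheap improvement to secondary safety data and does not touch the primary endpoint.

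**What to change.** 1. In sections VI.D and XVI.H, replace the qualified item for non-serious events, so that the list requires all serious adverse events and all adverse events of the operated limb, whether or not considered related to the device or procedure, collected identically in both arms.
2. Make relatedness a mandatory recorded field for each of these events, and state who completes it. Align the follow-up safety headings in section VIII.F so that they name both implants.
3. In section X.c, limit the sentence on characterising all events to the collected scope, and say that other unrelated non-serious events are not systematically collected.
4. Check the case report form and adverse event form against the revised list.

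The cost is one list edit made in two places, small text changes in sections VIII.F and X.c, and some extra short adverse-event forms for the site. No visit or examination is added.
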